APPENDIX 2. ADAPTATION OF TRIAL PROTOCOL DURING THE COVID-19 PANDEMIC

Background

The COVID-19 pandemic has caused significant disruption globally and is a public health emergency that has an impact on the conduct of global clinical research activities. The safety of patients and site staff continues to be paramount, and Alector has made the decision to continue patient participation in the AL001-ALS-201 study at the discretion of the investigator, and in accordance with each site's regional or country health authority guidelines and recommendations regarding the COVID-19 pandemic.

Alector, in collaboration with the CRO, is committed to performing pandemic-related risk reviews of study procedures and mitigating the effect of the pandemic on the conduct of this study. These ongoing collaborative risk reviews include analysis of COVID-19 restrictions as they impact patient safety, study, and data integrity, and the impact on program timelines continues to be assessed. The review has been and will continue to be conducted regularly and will take into consideration any new information regarding the pandemic, including continuous assessment of adverse events reported in the study.

Implementation of COVID-19 Adaptations

The implementation of adaptations to study visits and procedures described in this appendix applies only to the exceptional circumstances of the COVID-19 pandemic. Procedure adaptations apply to those sites that have been impacted by the pandemic through restrictions to movement/travel, study site restrictions, and where the safety of the patient may be adversely impacted by on-site visits.

The implementation of these adaptations will be determined on a site-by-site basis dependent on local requirements, and will be reviewed on a regular basis with Alector to confirm the continued need for implementation.

Essential On-Site Assessments and Remote Visits (Via Phone or Video)

Continuation of the study during the pandemic does, and will continue, to impact the ability of some sites to conduct all protocol assessments per the Schedules of Assessments. This is due to reduced time for on-site visits, limited or no availability of some services on site, and the need to conduct visits remotely via telephone or via televisit (if approved locally).

The primary objective with any change to the study schedule is to ensure ongoing monitoring of patient safety.

On-Site Essential Assessments

Where possible, all protocol assessments and treatments should be completed.

To accommodate reduced time on-site during study visits, the following reduced assessments schedule should be completed **as a minimum**:

- Vital signs, weight, physical, and neurological examinations
- Phlebotomy and urinalysis, including pregnancy test

- ECGs
- Collection of AEs and concomitant medications
- C-SSRS
- Study drug administration

Remote Essential Assessments

If patients or raters are not able to come to the study site for a visit, the following assessments should be completed by telephone or video (if locally approved/allowed):

- Review of AEs and concomitant medications
- Review of medical history
- ALSFRS-R
- C-SSRS

On-Site Assessments that Cannot be Completed at Scheduled Visits

In the event that a scheduled assessment cannot be completed at the site, eg, limited availability/restriction of equipment, patient has limited time on-site, or because a remote visit was completed, the missed assessments may be completed at a future on-site visit, as determined and approved by the Medical Monitor.

The approval of the Medical Monitor must be obtained prior to completion of these rescheduled assessments.

COVID-19 Reporting

In the event that a study subject is diagnosed with COVID-19 infection, the local health authority recommendations regarding treatment should be followed and the event should be reported as an AE/SAE, depending on the severity of infection and diagnosis.

Remote Consent

Where it is allowed by country/site regulations, a remote eConsent will be provided that allows a patient to be physically remote from the study site and participate in the consent process.

Remote Source Document Verification

Remote source document verification will be employed in the following circumstances:

- International law, regulatory authorities, and the IRB/IEC permit this process and on-site CRA visits are not permitted due to continued COVID-19 restrictions
- There is a need to complete source document verification for the following reasons:
 - Study data assessment review of critical study milestones (eg, database lock)
 - Patient safety
 - A significant backlog of data monitoring that could impact data integrity or patient safety

Prior to commencing remote source document verification, the following documentation must be completed, if required per local regulations:

- The site CRA will complete a confidentiality agreement committing to the following:

1. INTRODUCTION

Study AL001-ALS-201 titled “A Phase 2, Multicenter, Randomized, Double-Blind, Placebo-Controlled Study to Evaluate the Safety, Tolerability, Pharmacokinetics, and Pharmacodynamics of AL001 in C9orf72-Associated Amyotrophic Lateral Sclerosis” was halted early after 5 participants were enrolled. The study was not halted for safety reasons. Due to the limited number of patients enrolled, a synoptic clinical study report (sCSR) will be produced.

This statistical analysis plan (SAP) provides a brief description of the planned analysis and reporting to support the development of the sCSR. This SAP is based on Protocol version 3.0 dated 11 February 2022.

[figure not shown]
2. STUDY DESIGN

2.1. Design Overview

This is a Phase 2, multicenter, randomized clinical trial evaluating the safety, tolerability, pharmacokinetics (PK), and pharmacodynamics (PD) of AL001 compared to placebo in 5 adults with *C9orf72*-associated Amyotrophic Lateral Sclerosis (C9ALS). AL001 is hypothesized to protect motor neurons by increasing extracellular progranulin (PGRN) levels and thereby reducing TAR DNA-binding protein 43 (TDP-43) pathology in amyotrophic lateral sclerosis (ALS). The trial has been designed to confirm elevation of PGRN and accumulation of AL001 in cerebral spinal fluid (CSF) and to provide proof-of-mechanism target engagement in preparation for a larger trial testing the clinical efficacy of AL001 in C9ALS.

The study consists of a Screening Period (within 3 weeks prior to Day 0), a 24-week Treatment Period, and an 8-week Safety Follow-Up Period, concluding with the Study Completion Visit (8 weeks after last study drug administration). Day 0 is defined as the baseline, the first date of study drug administration.

Subjects will be randomly assigned to receive either standard of care + AL001 or standard of care + placebo in a 2:1 ratio with stratification by rs5848 genotype (3 levels: CC, CT, and TT). Randomization will use each stratum specific computer-generated permuted block randomization schedule with an undisclosed block size. Seven doses of AL001 60 mg/kg or matching placebo are planned to be administered via intravenous (IV) infusion every 4 weeks for 24 weeks (Visit 2 through Visit 8). Overview of Study Schema is shown below:

A subject is considered to have completed the study if he or she has completed all phases of the study including the last visit or the last scheduled procedures shown in the Schedule of Assessments. Subjects can withdraw from the study at any time. Subjects who plan to discontinue the study early should be encouraged to return to the investigational site for an Early Termination Visit, which is 8 weeks after the last dose of study treatment.

3. STATISTICAL METHODS

3.1. General Considerations

No formal statistical analyses are planned. Key data will be provided in listings. All listings will be produced at the completion of the study for the sCSR using SAS® software version 9.4.

Adverse events (AEs) will be coded using the Medical Dictionary for Regulatory Activities (MedDRA) version 25.0 for system organ class (SOC) and preferred term (PT). Severity AEs will be graded according to the World Health Organization (WHO) Toxicity Grading Scale, March 2020 or later. If an AE is not specified within the WHO Toxicity Grading Scale, then the AE will be graded according to the following definitions:

Grade	Severity	Description
1	Mild	Transient or mild discomfort; no limitation in activity; no medical intervention or therapy required. The subject may be aware of the sign or symptom but tolerates it reasonably well.
2	Moderate	Mild to moderate limitation in activity; no or minimal medical intervention or therapy required.
3	Severe ¹	Marked limitation in activity; medical intervention or therapy required; hospitalizations possible.
4	Life-Threatening	The subject is at risk of death due to the AE as it occurred. This does not refer to an AE that hypothetically might have caused death if it were more severe.
5	Death	Any AE where the outcome is death.

¹ Note that the term “severe” is a measure of intensity and that a severe AE is not necessarily serious.

Relatedness of each AE to the study treatment is assessed by the investigator as ‘Related’ or ‘Not Related’.

3.1.1. Baseline Definition

Unless otherwise specified, baseline value of a variable is defined as the last non-missing value prior to the first study treatment (Day 0).

3.2. Analysis Populations

3.2.1. Safety Analysis Set

All subjects who receive at least one dose of AL001 or placebo will be included in the Safety Analysis Set.

4. LISTINGS

All listings will use the Safety Analysis Set.

4.1. Subject Disposition, Demographics

Subject demographics and rs5848 genotype (age, sex, ethnicity, race, screening weight, genotype) and disposition (study drug completion status, and study completion status) will be listed.

4.2. Exposure to Study Drug

Doses of AL001 or placebo are planned to be administered IV over 60 minutes (± 15 minutes) by trained site personnel under the supervision of the investigator or their designee. Study treatment administration are recorded in the source documentation and in the electronic Case Report Form (eCRF), in particular planned infusion volume, actual infusion volume, and start and stop times of infusion, if the infusion was interrupted and if yes, reason for interruption.

Exposure to study drug will be listed for the Safety Analysis Set.

4.3. Protocol Deviations

A protocol deviation occurs when the subject, investigator, or Alector (or designee) fails to adhere to protocol requirements. Important protocol deviations are the ones that affect the subjects' safety or the primary endpoint (safety). Important protocol deviations for this study include, but are not limited to, the following:

- Failure to meet inclusion/exclusion criteria
- Failure to comply with Good Clinical Practice (GCP) guidelines will result in an important protocol deviation; Alector will determine if an important protocol deviation will result in withdrawal of a subject from the trial.

All important protocol deviations will be listed.

4.4. Adverse Events

AEs are collected regardless of cause or relationship that occur after signing of informed consent through end of study visit. Treatment emergent adverse events are those AEs with a start date on or after the date of first administration of investigational product. All AEs will be listed with a flag to indicate if an AE is treatment emergent.

In addition, all serious adverse events (SAEs) and AEs leading to discontinuation of study medication will be listed, with a flag to indicate if an AE is treatment emergent.

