8.1. Definition of Adverse Event

Adverse events are any untoward medical occurrence in a subject enrolled into this study, including side effects, injury, toxicity, sensitivity reaction, intercurrent illnesses, clinically significant physical exam signs, or sudden death, whether or not it is considered related to the study treatment. Subjects will be instructed to contact the investigator at any time after informed consent if any symptoms develop. Subjects will be instructed to report all AEs to the investigator. All AEs must be appropriately documented in the subject's original source documents and on the eCRFs. Investigators should report the diagnosis rather than list symptoms, whenever possible.

A treatment-emergent AE (TEAE) is defined as any event not present before first administration of study treatment or any event already present that worsens in either intensity or frequency after first administration of study treatment.

Adverse events resulting from concurrent illnesses, reactions to concurrent illnesses, reactions to concurrent medications, or progression of disease states must also be reported within the established time frames.

An AE does not include the following:

- Elective medical or surgical procedures planned prior to the start of study treatment (eg, hip replacement surgery) that did not result from a worsening of a previous condition (ie, prior to signing informed consent). *Note:* Any serious procedural complication or hospital-emergent conditions (eg, nosocomial infection) would be reported as an SAE.
- Any medical condition or clinically significant laboratory abnormality that has an onset date before the consent form is signed, and that is not related to a protocol-associated procedure, is not an AE. Such conditions are considered to be pre-existing and should be documented on the medical history eCRF. A pre-existing condition should be reported as an AE only if its frequency, intensity, or symptoms worsen during the course of the study.
- Situations where an untoward medical occurrence has not occurred (eg, hospitalization for study treatment administration per institutional guidelines, elective surgery, social and/or convenience admissions).

- Overdose without adverse event.
- Disease progression within expected parameters for the study population is not considered an AE. See [Section 8.3](#) for Protocol Specific Disease Progression Adverse Event and Serious Adverse Event Reporting Requirements.

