8.5. Assessment of Adverse Events

8.5.1. Assessment of Adverse Event/Serious Adverse Event Severity

The severity, or intensity, of an AE refers to the extent to which an AE affects the subject’s daily activities. Severity will be graded according to the World Health Organization (WHO) Toxicity Grading Scale, March 2020 or later. If an AE is not specified within the WHO Toxicity Grading Scale, then the AE will be graded according to the following definitions:

Grade	Severity	Description
1	Mild	Transient or mild discomfort; no limitation in activity; no medical intervention or therapy required. The subject may be aware of the sign or symptom but tolerates it reasonably well.
2	Moderate	Mild to moderate limitation in activity; no or minimal medical intervention or therapy required.
3	Severe*	Marked limitation in activity; medical intervention or therapy required; hospitalizations possible.
4	Life-Threatening	The subject is at risk of death due to the AE as it occurred. This does not refer to an AE that hypothetically might have caused death if it were more severe.
5	Death	Any AE where the outcome is death.

Abbreviation: AE=adverse event.

*Note that the term “severe” is a measure of intensity and that a severe AE is not necessarily serious.

Changes in the severity of an AE should be documented to allow an assessment of the duration of the event at each level of intensity to be performed. AEs characterized as intermittent do not require documentation of onset and duration of each episode. When the intensity of an AE changes more than once a day, the maximum severity for the event should be listed. If the intensity changes over a number of days, these changes should be recorded separately (ie, as having distinct onset dates).

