9.3.6. Safety Analyses

9.3.6.1. Safety

Safety will be assessed by the occurrence of TEAEs, treatment-emergent SAEs, and treatment-emergent clinically significant abnormalities in clinical and laboratory values. AEs will be coded to system organ class and preferred term using the MedDRA Version 22.0 or later and summarized as counts of events and proportions of subjects experiencing a given type of event, by treatment group.

Summaries by severity, relationship to the study intervention, action taken with respect to study intervention, and outcome of all TEAEs will also be provided, by treatment group.

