¹⁶ ALS Functional Rating Scale-Revised.

¹⁷ Pulmonary function testing (PFT) includes slow vital capacity (SVC) at in-clinic study visits and FVC and forced expiratory volume in one second (FEV1) when conducted in a PFT lab. In addition to this in-clinic assessment, home spirometry will be performed with virtual coaching by study staff within 2 days of each in-clinic study visit. The initial home spirometry assessment will be performed in clinic with study staff at the Baseline visit with retest at home with virtual coaching by study staff within 2 days after the Baseline visit.

¹⁸ ALS Cognitive Behavioral Scale.

¹⁹ C-SSRS Baseline Version to be completed at Baseline Visit only. C-SSRS Since Last Contact version to be completed at all other visits.

²⁰ Digital monitoring to occur approximately weekly. Subjects will undergo set up of digital monitoring smartphone application and initial use with study staff during the Baseline Visit. All subsequent weekly digital monitoring should occur at home and before noon, if possible, to minimize the potential effects of fatigue. At every in-person visit after Baseline study staff will check-in on subject use and app-related questions.

²¹ Adverse events that occur AFTER signing consent form will be recorded.

²² AL001 should be infused over 60 minutes, with a 60 minutes observation period following infusion completion for the first 2 infusions (30 minutes for subsequent infusions). In the event of an infusion-related reaction, blood will be drawn for PK serum and ADA assessment of AL001 or placebo; the following laboratory tests should be drawn: CRP, ferritin, tryptase, and IL-6 (at 1 to 2 hours after the IRR, then again at 48-72 hours after the IRR). Where possible, clinical laboratory samples should be drawn at the site for the central laboratory; however, local laboratories may be utilized and results assessed for safety by the investigator.

²³ Administer first dose of study drug AFTER Baseline Visit procedures are completed.

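### SAP 4.4 flags treatment-emergent AEs by start date alone and omits the protocol's worsening criterion, so a pre-dose AE that becomes more frequent on treatment can be flagged as not treatment-emergent

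*SAP*

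**What the plan says.** SAP 4.4 collects AEs from consent onward ("AEs are collected regardless of cause or relationship that occur after signing of informed consent through end of study visit") and classifies them by one test: "Treatment emergent adverse events are those AEs with a start date on or after the date of first administration of investigational product". The flag is attached to the listing of all AEs, and also to SAEs and to AEs leading to discontinuation of study medication.

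Protocol 8.1 has two limbs. An AE is treatment-emergent if it was absent before the first administration, or if it is "any event already present that worsens in either intensity or frequency after first administration of study treatment". On conditions that pre-date consent, the same section adds: "A pre-existing condition should be reported as an AE only if its frequency, intensity, or symptoms worsen during the course of the study".

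Protocol 8.5.1 sets the recording rules that decide what start date an AE carries. A change in intensity that takes place over several days becomes a separate record with its own onset. For intermittent events the rule is looser: "AEs characterized as intermittent do not require documentation of onset and duration of each episode".

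SAP section 1 says the SAP is based on protocol version 3.0. It does not announce a changed definition of treatment emergence.

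**The concern.** A start-date test and a worsening test agree only if every worsening produces a new start date. The protocol arranges this for intensity but not for frequency. An AE that starts before dosing and recurs more often on drug meets the protocol's definition, yet the SAP can label it as not treatment-emergent.

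The label bears on a primary outcome. Protocol 9.3.6.1 states: "Safety will be assessed by the occurrence of TEAEs, treatment-emergent SAEs, and treatment-emergent clinically significant abnormalities in clinical and laboratory values". Tolerability, also primary, turns on treatment-emergent AEs that lead to stopping treatment. With listings only, the flag is the SAP's sole marker of treatment emergence, so a sentence in the synoptic report about such events would probably be drawn from it.

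**Working it through.** No figure in the plan needs to be reproduced. The check sets the two definitions beside the recording rules.

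**Inputs**
- SAP rule: start date on or after the date of first dose (SAP 4.4).
- Protocol rule: not present before first administration, or present and worse in intensity or frequency afterwards (protocol 8.1).
- Recording of intensity: a change over days gets a distinct onset date (protocol 8.5.1).
- Recording of frequency: no rule, and no onset needed for each intermittent episode (protocol 8.5.1).
- Collection starts at consent (SAP 4.4; protocol Appendix 1, footnote 21), and screening may run for up to 21 days before Baseline (Appendix 1, footnote 1). AEs with pre-dose onset can therefore enter the listings.

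**Both rules applied to constructed patterns** (TE = treatment-emergent)

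| Pattern | Protocol 8.1 | SAP 4.4 |
|---|---|---|
| New AE after first dose | TE | TE |
| Onset between consent and first dose, no later change | Not TE | Not TE |
| Pre-dose onset; intensity worsens over days after dosing; separate record | TE | TE, on the new record |
| Pre-dose intermittent AE; only frequency rises; site opens a new record | TE | TE |
| Pre-dose intermittent AE; only frequency rises; single record kept | TE | **Not TE** |
| Pre-consent condition that first worsens after dosing | TE | Depends on the start date entered |
| Onset on Day 0 before the infusion, no worsening | Not TE | **TE** |

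The fifth row is the main point. Protocol 8.5.1 does not forbid a new record when frequency rises, but it does not ask for one. A site that follows the protocol exactly can therefore produce this mismatch.

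The sixth row cannot be settled from the documents. Such a condition becomes an AE only on worsening, so it may well be dated at the worsening. No dating convention is stated, however, and if the original onset is entered the SAP rule misses it.

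The seventh row is a mismatch in the opposite direction. The SAP compares dates, while the protocol refers to the first administration itself. Appendix 1, footnote 23 places the first dose after the Baseline procedures, so a Day 0 onset before the infusion is possible.

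The patterns test the logic of the rules. How many of them disagree says nothing about how often disagreement would occur.

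**The case against.** The strongest reply is that almost nothing follows from the gap. SAP sections 1 and 3.1 describe a study halted after 5 enrolled, a synoptic report, listings and no formal analysis. The counts and proportions by treatment group in protocol 9.3.6.1 are not produced under this SAP, and protocol 9.3.1 leaves analysis details to the SAP. Every AE appears whatever its flag. This stands, and it sets the size of the finding. It does not make the two definitions agree, because leaving details to the SAP does not extend to contradicting protocol 8.1 without saying so.

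A second reply is that protocol 8.5.1 ties severity to the effect on daily activities. A rise in frequency that matters clinically would often raise the grade and so gain its own onset date. This also stands in part: it narrows the case mainly to rises in frequency without a change of grade, which are less likely to become serious or lead to discontinuation. But protocol 8.1 names frequency as a criterion separate from intensity, so the grading route does not replace it.

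A third reply is that a retrospective review may find nothing usable. Protocol 8.6.1 requires a nonleading question at each visit about changes in well-being, not a count of episodes. This is a fair limit on the review, though not on correcting the definition.

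**Conclusion.** The point holds as a minor inconsistency, at the lower end of that grade. SAP 4.4 omits one limb of the protocol's definition, and the recording rules leave at least one route by which the omission changes the flag. The effect is confined to the flag in the AE listings and to any statement in the synoptic report that relies on it. The conclusion assumes that the listings are programmed as SAP 4.4 is written and that sites use the latitude protocol 8.5.1 gives for intermittent AEs.

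A reader might infer more than the documents support:
- *That all worsening is missed.* It is not; the 8.5.1 rule on distinct onset dates means most worsening in intensity is still flagged.
- *That frequency-only worsening is the only mismatch.* This is not established. Besides pre-consent conditions and Day 0 onsets, 8.5.1 asks only for maximum severity when intensity changes more than once a day, so some worsening in intensity may also leave no new date.
- *That exposure is bounded by the three-week screening period.* It is not. Rescreening under protocol 4.3 requires a second consent, so the time from first consent to dosing can be longer, and a pre-consent condition might carry an older start date.
- *That events are lost or a rate is biased.* Neither follows, since all AEs are listed and no incidence is calculated.

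The documents give neither AE counts nor the number of participants dosed, so the number of affected events, which may be zero, cannot be estimated.

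**What to change.** Replace the SAP 4.4 sentence with the two-limb definition of protocol 8.1: absent before first administration, or already present and worse in intensity or frequency after it. State how the start date is assigned when a pre-consent condition worsens, and how a Day 0 onset is placed relative to the infusion.

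Then review the AEs with onset before first dose for later worsening in intensity or frequency, using the source records from each visit. Do this without reference to treatment assignment where possible, and flag those that worsened as treatment-emergent. Where frequency was not documented, leave the flag unchanged and say so in the listing. If the listings are already final, a note in the synoptic report naming the rule used would at least make the difference visible.

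The cost is a short change to SAP 4.4 and a brief manual review in a study with 5 enrolled. The review may be inconclusive for some events.
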